MATCHING. Cases and controls will be individually matched to enhance study efficiency and precision with more stable odds ratio estimates and narrower confidence intervals. Matching will be based upon factors which are biologically strong confounders as follows: 1) age (\pm 5 years), 2) gender, 3) race (*white* versus *non-white*) and 4) obesity (BMI $+\text{-}2$ kg/m^2). Recruitment of controls and cases will be contemporaneous given concurrent assessments of eligibility (AF status and matching criteria). To ensure appropriate individual matching on the factors listed above, a staggered recruitment of controls will occur such that matching parameters will change monthly depending upon the distribution of these factors in the case group. Statistical code will be written to perform matching of cases and controls with these five

Elucidation of the Influence of Sleep Apnea on Risk of Atrial Fibrillation PI- [name] and [name]

variables. If exact control matches are not identified, then unmatched cases will be retained in the cue until the next round of matching.

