SA 1. Quantify the extent that SDB and its subtypes are associated with PAF. This aim will be addressed by fitting conditional logistic regression models that condition on the matched pair. We will separately analyze each SDB variable (primary variable: AHI) to obtain an estimate and 95% CI of the odds ratio of PAF for a 1-unit increase in the SDB exposure. Non-linear effects between SDB and the log odds of PAF will be assessed using restricted cubic splines. Knots for the spline will be based on the SDB threshold at which PAF risk increases. Unadjusted and hierarchical adjusted models will be performed using the covariates listed above.

The secondary exposure variables (e.g. hypoxia, OAHI, CAI, AI) will be considered in separate models.

Exploratory Aim 1a. Cardiac structure, autonomic and biochemical variables (Table 2) will explain a proportion of the SDB and PAF relationship. This aim will be addressed by applying Pearl's mediation formula ¹⁰⁸ to the conditional logistical regression model. This approach will allow a causally sound definition of the mediation effect of a given intermediate variable in the relationship between SDB (defined by AHI) and PAF. The approach involves a model for each mediator (e.g. a general linear model for a continuous mediator) and possibly a random effect to account for clustering due to matching and can be thought of as a generalized structural equations model. This approach will allow us to simultaneously assess multiple mediators and will also allow us to consider AHI as a continuous variable. Each model will be fit using likelihood methods and model fit will be checked using appropriate information criteria. After fitting the overall model, we will obtain, for each mediator, an estimate of the indirect effect (e.g. the portion of the overall effect of SDB on PAF mediated through the intermediate variable). A bootstrap resampling technique will be used to obtain a 95% CI for each indirect effect. If the CI does not contain zero, this will indicate statistically significant mediation.

Exploratory Aim 1b. Explore age interactions in the SDB-PAF relationship. Each conditional logistic regression model will include an interaction between age and SDB to investigate if age is a modifier of the effect of SDB on PAF, i.e. whether the odds ratio of PAF for a 1-unit increase in SDB varies by age.

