SA2. Examine patterns of PAF burden via 7-21 day continuous ECG monitoring relative to SDB. We will model the relationship between mean frequency AF paroxysm variation and SDB (e.g. AHI considered as a continuous variable). A linear regression model will be used to assess possible quadratic and threshold effects of SDB on variation. These models may also include sleep state by SDB interaction terms (along with the state indicator) to examine if the effect of SDB on variation differs by sleep state. Maximum likelihood (based on a normal distribution for variation if appropriate) will be used to fit models, and the Akaike Information Criterion (AIC) will be used to select the best fitting model. Estimates of the effect of SDB on variation (and corresponding 95% CI) will be obtained based on the selected model.

SA3. Examine the effects of SDB (AHI \geq 15) treatment for 3 months on AF paroxysm frequency and also measures of autonomic function, cardiac morphology, biochemical measures in those with SDB and PAF. For this subgroup of SDB (AHI \geq 15) and PAF, we will perform paired t-tests to compare pre- and post-treatment mean outcomes (Primary outcome: AF paroxysm frequency from 1-week ECG monitoring) and also ECHO and biochemical measures. For any outcome for which a departure in normality is found (based on the Shapiro-Wilk test) but a transformation of the outcome cannot be found to adequately address the issue, we will use the Wilcoxon signed rank sum test to detect a difference in the distribution of the pre- and post- responses. This assessment is not intended to be confirmatory, but rather to provide estimates of variability and effect sizes to inform future studies/randomized trials. Linear regression models will then be developed to model PAF burden at the 3 month visit by conditioning on baseline PAF burden, baseline SDB,

and time from baseline to 3 month visit. Additional adjusted models will carefully consider the covariates list above.

POWER BY AIM.

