SA 1. A sample size of 300 will be able to detect an odds ratio of 1.50 with 80% power (and 1.60 with 90% power), assuming a 2-sided alpha level of 0.05, a correlation in AHI between cases and controls of zero and a probability of PAF of 0.20 when AHI is set at its mean value. Note that the odds ratio is interpreted as the odds ratio for PAF for a 1 standard deviation increase in AHI. Alternatively assuming that the probability that $AHI \geq 15$ for patients without PAF is 30% ⁶⁴, a sample size of 150 matched pairs will be able to detect an odds ratio of PAF of 2.13 with 90% power assuming a 2-sided alpha-level of 0.05. Note that this calculation assumes that the correlation for SDB between subjects with and without PAF is 0.20, as suggested by Dupont (1988)¹⁰⁹ when the correlation is unknown. Our prior cross-sectional work demonstrating SDB-AF odds ratio point estimates of 2-4 ^{1,2} supports sufficient power to address this aim.

Exploratory Sub-Aim 1a. To calculate the power to detect mediation, a difference in coefficients approach will be used ¹¹⁰ which involves the fitting of two logistic regression models that model the association between SDB ($AHI \geq 15$) and the log odds of PAF (one with and the other without the potential mediator in the model) to estimate the proportion of exposure effect that is mediated. Assuming a correlation between the adjusted and unadjusted effect estimates of 0.9 and that the probability of PAF in SDB and no SDB is 0.07 and 0.01 respectively (based upon prior data ²), a sample size of 150/group will be able to detect mediation proportions of 0.5 with 84% power assuming a 2-sided 0.05 alpha-level test. Although power may be reduced depending on the observed imbalance in sample sizes for the SDB and no SDB groups, power will be increased due to matching (not taken into account here to be conservative).

SA2. Using a two-sample t-test (2-sided 0.05 alpha-level) to test for a difference in mean variation between the SDB ($AHI \geq 15$) and no SDB groups, a sample size of 150 (75 with SDB and 75 without SDB) will detect mean differences within 0.46 standard deviations with 80% power and 0.53 standard deviations with 90% power.

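### SA2 specifies no covariate-adjusted model, so its case-only estimate of the SDB effect on AF burden is open to confounding by age, sex, race and BMI.

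*Combined protocol and SAP*

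**What the plan says.** The analytic text appears twice, in section 9 (Analytic Plan) and section 10 (Data Analysis), and the two agree on this point.

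- **SA1**, conditional logistic regression on matched pairs: "Unadjusted and hierarchical adjusted models will be performed using the covariates listed above".
- **SA3**, pre-post comparison and then regression: "Additional adjusted models will carefully consider the covariates list above".
- **SA2**, linear regression of paroxysm frequency on SDB with possible quadratic and threshold terms. The only other terms named are optional: "These models may also include sleep state by SDB interaction terms (along with the state indicator"). AIC chooses among the models, and then "Estimates of the effect of SDB on variation (and corresponding 95% CI) will be obtained based on the selected model". No covariate and no adjusted model is mentioned.

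The covariate list stands under its own general heading, after an outcome list that includes AF burden for SA2 and SA3. It holds age, race, BMI, cardiac drugs, left atrial volume and LVEF among others. Sex is not in it.

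Section 5 (Matching) says: "Matching will be based upon factors which are biologically strong confounders as follows", and gives age, gender, race and BMI. The matching pairs a case with a control. SA2 is confined to participants with PAF (section 1, aims). The SA2 power statement is also unadjusted: "Using a two-sample t-test (2-sided 0.05 alpha-level) to test for a difference in mean variation between the SDB" and no-SDB groups.

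**The concern.** The three aims differ in how they are protected against confounding. SA1 has matching and adjusted models. SA3 compares each patient with himself or herself and then adds adjusted models. SA2 compares different patients with different SDB severity, and it has neither. Pairing a case with a control of similar age and BMI does nothing to make cases with high AHI resemble cases with low AHI.

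Section 3 of the protocol gives grounds for caution. It ties SDB to obesity, and it cites a graded relation between BMI and progression from paroxysmal to permanent AF. If BMI or age relates to both AHI and paroxysm frequency among cases, the SA2 coefficient absorbs part of that relation. AIC does not guard against this, because it ranks models by fit and not by control of confounding, and no covariate is required in the models it compares. SA2 is listed as one of three primary aims, so a misattributed association would be a main result.

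**Working it through.** **1. The plan's own figures.** Inputs from the SA2 power statement: two-sample t-test, two-sided alpha 0.05, 75 per group. By the noncentral t with 148 df, 0.46 SD gives 79.9% power and 0.53 SD gives 89.7%. This agrees with the plan: "a sample size of 150 (75 with SDB and 75 without SDB) will detect mean differences within 0.46 standard deviations with 80% power". The larger difference that the plan gives for its 90% target reproduces too. There is no arithmetic error.

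**2. Size of the confounding risk.** The documents give no correlation of any covariate with AHI or with burden among cases, so the inputs here are assumptions. Take one omitted standardized covariate, with correlation r to AHI and effect b (in SD) on burden, and no true SDB effect. AHI is continuous, as in the SA2 model.

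- Spurious AHI-burden correlation: p = r × b.
- Noncentrality: p × √148 / √(1 − p²).
- Rejection rate ≈ Φ(nc − 1.96) + Φ(−nc − 1.96).

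| r (AHI-covariate) | b (covariate-burden) | p | noncentrality | rejection at nominal 5% |
|---|---|---|---|---|
| 0.1 | 0.1 | 0.01 | 0.12 | 5.2% |
| 0.2 | 0.2 | 0.04 | 0.49 | 7.8% |
| 0.3 | 0.2 | 0.06 | 0.73 | 11.3% |
| 0.3 | 0.3 | 0.09 | 1.10 | 19.6% |
| 0.4 | 0.3 | 0.12 | 1.47 | 31.3% |
| 0.5 | 0.3 | 0.15 | 1.85 | 45% |

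The noncentral t with 148 df gives nearly the same values (45.0% in the last row). With weak correlations the inflation is negligible; with moderate ones it is several-fold.

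**3. Effect of adjustment on precision.** Let R²y be the share of outcome variance, and R²x the share of SDB variance, that the covariates explain. Adjustment multiplies the detectable difference by √((1 − R²y)/(1 − R²x)). Adjusting for one covariate such as BMI, with R² equal to the squared correlation:

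| AHI-BMI | BMI-burden | factor | power at 0.46 SD |
|---|---|---|---|
| 0.3 | 0.3 | 1.00 | 79.9% |
| 0.3 | 0.2 | 1.03 | 77.8% |
| 0.5 | 0.3 | 1.10 | 71.9% |
| 0.5 | 0.2 | 1.13 | 69.6% |

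For example, in the last row √(0.96/0.75) = 1.13, and 0.46/1.13 = 0.41 SD. Power rises only when covariates explain more of the burden than of SDB. With R²y 0.30 and R²x 0 it is 91.7%; with R²y 0 and R²x 0.30 it is 64.9%. The documents do not say where in that range the study lies.

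**4. Degrees of freedom.** Spending about 20 moves power at 0.46 SD from 79.9% to 79.8%, so this cost can be ignored.

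**The case against.** The strongest reply is that the covariate list is general. It is not limited to SA1 and SA3, it follows an outcome list that names SA2, and the phrase that models may also include sleep-state terms does not exclude others. On that reading only a cross-reference is missing. This stands to the extent that one cannot infer that SA2 will be unadjusted. It does not remove the gap. SA2 alone fails to invoke the list, and even if the list applies, nothing says which covariates enter or whether they must survive AIC selection.

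A second reply is that confounding is not demonstrated, and that is correct. Section 5 calls the matching factors confounders in the setting of PAF status, not of paroxysm frequency among cases. The cited BMI evidence concerns progression to permanent AF. Section 3 also reports higher odds of arrhythmia at younger age, so the direction for age is not obvious. A drug that changes paroxysm frequency confounds only if its use also relates to AHI, and the documents do not show that it does. A reader might infer that the SA2 estimate is confounded; the documents support only that it is open to confounding.

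A reader might also infer that leaving covariates out costs SA2 power. That is not supported. Under the BMI correlations of 0.3 or more with AHI in step 3, adjusting for BMI never raises power above the unadjusted 79.9%. Gains need covariates that predict burden but are largely unrelated to SDB, and no figure in the documents establishes any.

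**Conclusion.** The point holds as a gap in specification with a real risk of bias. SA2 names no adjusted model, takes its estimate from an AIC-selected model in SDB and sleep state, and gets no balance from the case-control matching. The rejection rate under a true null runs from about 5% to about 45% over the assumed correlations. That range describes sensitivity to unknown inputs and is not a prediction for this study. It rests on a single linear confounder, 150 cases and a normal outcome. The case rests on bias alone and not on precision. The change is worth making because it is cheap and SA2 is a primary aim.

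**What to change.** In the SA2 text of sections 9 and 10:

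1. Make the main model paroxysm frequency on AHI adjusted for age, sex, race and BMI. Keep these four in every linear, quadratic, threshold or sleep-state model that AIC compares. Name sex explicitly: it is a matching factor but is not in the covariate list, so a pointer to the list would leave it out.
2. Report the unadjusted model as supportive.
3. Add anti-arrhythmic and rate-controlling drug use in a prespecified further model and not in the main one. Treated cases whose PAF continues are eligible, so use will vary, but drug use may be a response to AF burden.
4. Keep left atrial volume and LVEF to a separate step, because Table 2 treats them as mediators for SA1.

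The cost is plan wording and a few degrees of freedom, using variables the study already plans to collect. The real downside is a wider AHI interval if BMI and AHI are strongly correlated: at an AHI-BMI correlation of 0.5, power at 0.46 SD could fall to about 70%.

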Data generated from this research is key for developing new strategies to reduce AF-related morbidity including stroke, heart failure and also death. Expected results will be of high impact given ability to identify and inform future screening and treatment approaches for management and/or prevention of AF and identify key outcomes for clinical trials.

The primary aims of the study are to:

SA 1. Quantify the extent that SDB and its subtypes are associated with PAF. SDB will be assessed by the standard metric: the Apnea Hypopnea Index (AHI) and also Central Apnea Index, Periodic Breathing, Obstructive Apnea Hypopnea Index and % sleep time $<90\%$ SaO $_2$. For each, exposure response relationships and thresholds that confer increased risk for PAF will be defined.

Elucidation of the Influence of Sleep Apnea on Risk of Atrial Fibrillation PI- [name] and [name]

SA 2. Examine PAF burden (defined as frequency of paroxysms over a 24 hour period and average duration of paroxysms) via 7-21 day continuous ECG monitoring relative to SDB in those with PAF.

SA 3. Examine the effects of SDB (AHI \geq 15) treatment for 3 months on PAF burden and also measures of autonomic function, cardiac morphology and biochemical measures in those with SDB and PAF.

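### SA2 picks the AHI dose-response shape by AIC and then reports that model's ordinary 95% CI, so under no SDB effect an effect would appear in more than 5% of studies

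*Combined protocol and SAP*

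**What the plan says.** The SA2 paragraph under Analytic Method by Aim, in section 10 (Data Analysis), takes AHI as continuous and states: "A linear regression model will be used to assess possible quadratic and threshold effects of SDB on variation". It adds an option: "These models may also include sleep state by SDB interaction terms". The choice among these models is made on the study data: "the Akaike Information Criterion (AIC) will be used to select the best fitting model". Reporting follows from that choice: "Estimates of the effect of SDB on variation (and corresponding 95% CI) will be obtained based on the selected model". Section 9 (Analytic Plan) has the same selection and reporting sentences.

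The text does not list the candidate models, fix the number or position of thresholds, or say whether a threshold is a step or a change of slope. It does not say whether a model without SDB is a candidate. No joint test, sample split or bootstrap is named for SA2. The bootstrap in the plan belongs to the mediation analysis in Exploratory Aim 1a.

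The SA2 power statement uses a different analysis: "Using a two-sample t-test (2-sided 0.05 alpha-level) to test for a difference in mean variation between the SDB" and no-SDB groups, split at AHI 15. SA2 is one of three aims introduced in section 1 by "The primary aims of the study are to".

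**The concern.** The same 150 patients choose the shape and supply the interval. A straight line and a step at a given cut each spend one coefficient on SDB, so AIC penalises them equally and keeps whichever has the smaller residual sum of squares. That is the one with the larger absolute t statistic and the smaller p-value. The ordinary CI from the winner is therefore the most favourable of several, presented as if it were the only one fitted. A step whose position is also chosen from the data makes this worse, unless the choice of cut is charged as a parameter.

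Two results are at stake: the stated precision of the SDB–AF burden association, and any AHI threshold reported with it. A threshold that reflects noise could be carried into later work as a finding.

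**Working it through.** **The plan's own figure.** For two groups of 75, the detectable difference in SD units is (z₀.₉₇₅ + z_power) × √(2/75), and √(2/75) = 0.1633.

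- 80% power: (1.960 + 0.842) × 0.1633 = 0.458, stated as 0.46.
- 90% power: (1.960 + 1.282) × 0.1633 = 0.529, stated as 0.53.

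The exact t calculation (148 df) gives 79.9% and 89.7%. So both stated figures, including "a sample size of 150 (75 with SDB and 75 without SDB) will detect mean differences within 0.46 standard deviations with 80% power", reproduce, but for a single fixed comparison with no model selection.

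**A bound for the selected model.** If the winner is significant, at least one candidate is. With m candidates each tested at 0.05, the false-positive rate is therefore at most 0.05 × m:

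- linear and quadratic, m = 2: at most 10%;
- plus one threshold, m = 3: at most 15%;
- plus three thresholds, m = 5: at most 25%;
- plus five thresholds, m = 7: at most 35%.

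The candidates are correlated, so the true rates are lower and were simulated.

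**Simulation inputs.** From the documents: n = 150, normal-theory regression, AIC selection, and AHI 15 as the cut in the SA2 power statement. Assumed: no SDB effect; log-normal AHI (median 15 with log-SD 0.9, or median 14 with log-SD 1); a standard normal outcome; the menus below; and a searched cut that is not counted as an AIC parameter. In each run the lowest-AIC model was kept and its SDB terms were judged by the overall F-test at 0.05. Where run counts are recorded, there were 2,000 to 8,000 runs per scenario. With 4,000 runs the standard error at a 10% rate is √(0.10 × 0.90/4000) = 0.5 percentage points. Ranges show the spread over separate simulations.

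| Candidate menu | Rate under no effect |
|---|---|
| Linear only, pre-specified | 4.9–5.0% |
| Linear, quadratic | 7.5–8.7% |
| Plus one step at AHI 15 | 9.9–10.4% |
| Plus one hinge (change of slope) at AHI 15 | 8.2% |
| Plus steps at 5, 15, 30 | 17% (16.0% in one repeat) |
| Plus steps at 5, 10, 15, 20, 30 | 19–20% |
| Plus a step searched over the 10th–90th percentiles | 33% on a 17-point grid (31.9% in one repeat), 34%, 38%, and 42% over every observed value |

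The spread in the last row was not reconciled; fineness of the search may explain it.

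**Sensitivity.**

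- *Form of threshold.* Hinges give 8.7% with cuts at 5, 15 and 30, and 9.8% searched. A linear term plus a step gives 9.7%, 13.4% and 27.6% (cut at 15; three cuts; searched). A linear term plus a hinge gives 9.4%, 11.9% and 14.3%.
- *No-SDB model in the AIC set.* 10.4% for the step at 15; 31% searched.
- *AHI spread.* Log-SD of 0.6 or 1.2: 10.3% and 10.0% for the step at 15.
- *Log-normal outcome with CV 1.5.* 10.1% for the step at 15; 30% searched.
- *Optional sleep-state interactions*, assuming two independent records per person. 15% for the step at 15, 24% for three steps, 44% searched.
- *Any SDB coefficient's CI excluding zero, instead of the F-test.* 12.4% for the step at 15. A pre-specified quadratic alone gives 7.4% on this reading, so part of that excess is not due to selection.

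**The case against.** The strongest objection concerns size. The plan never says that cut-points will be searched or that several will be tried, and the only SDB cut attached to SA2 is AHI 15. Section 1 does promise that risk thresholds will be defined, but under SA1 and for the presence of PAF. A reader might infer that SA2 will declare false effects a fifth or a third of the time. The documents do not support that, because those rates need menus that the plan does not state. This part of the objection stands.

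Second, SA2 contains no test or decision rule. Exploratory Aim 1a says what a CI that excludes zero will mean; SA2 does not. This also stands: the 5% benchmark is borrowed from the 95% level of the interval and from the power statement.

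Third, being listed as a primary aim does not make SA2 confirmatory, since SA3 is in the same list and is expressly described as non-confirmatory. That is fair as far as it goes. But the disclaimer is written for SA3 only, and an exploratory aim that reports a 95% CI still needs the interval to mean what it says.

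Fourth, only the no-effect case was simulated. A reader might infer a general coverage failure of the same size when an SDB effect exists; nothing here measures that.

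None of these points removes the defect. Every menu tried that involved selection exceeded 5%.

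**Conclusion.** The point holds. SA2 takes an uncorrected 95% CI from a model chosen by AIC on the same data, from an unlisted set. Under no SDB effect the nominal 5% becomes about 8–10% with linear, quadratic and one threshold fixed at AHI 15, and that range covers every form of threshold tried at that cut. It becomes about 17–20% with three to five step cut-points and about 33–42% with a searched step. Both larger ranges are specific to a step used alone; hinges, or thresholds added to a linear term, gave less. All figures assume log-normal AHI, n = 150 and an overall F-test. The low end is the case closest to the documents; the high end shows what the present wording leaves open.

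**What to change.** Before analysis, amend the SA2 text in sections 9 and 10 as follows.

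1. Name one primary model, for example a single linear term in AHI, and take the headline estimate and 95% CI from it whatever AIC prefers.
2. List the candidate shapes and cut-points. Say whether a threshold is a step or a change of slope, whether a no-SDB model is included, and whether the sleep-state interactions are part of the set.
3. Report the AIC-selected shape as exploratory, with an interval from a bootstrap that repeats the whole selection, including any search for a cut, in each resample.

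Listing the menu and fixing one cut at 15, without steps 1 and 3, would still leave about 8–10%.

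The cost is plan wording and a bootstrap loop, with no new data. The headline model may not be the best-fitting shape, but the selected shape is still reported beside it. Since the power statement rests on a two-group comparison at AHI 15, it should be restated if the primary model is continuous.

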3. BACKGROUND AND RATIONALE

3. A. 1. Atrial Fibrillation: Burgeoning Epidemic and Need for New Prevention and Treatment Approaches. AF is the most common sustained arrhythmia ³, affecting ~2.2 million individuals in the US ⁴, and potentially up to 16 million Americans by the year 2050 ⁵. AF is an independent predictor of mortality ⁶ and increased stroke, implicated in ~75,000 strokes per year ⁷. Annual costs for AF treatment have been estimated at \$6.7 billion, including \$2.9 billion for hospitalizations ⁸. Therefore, improved AF disease management strategies are needed to reduce hospitalizations and costs ⁹. Furthermore, AF treatments such as ablation and anti-arrhythmic medications are fraught with inconsistent results and pro-arrhythmic side effects ¹⁰. There is a critical need to identify alternative AF treatment and prevention strategies such as those targeting SDB.

3. A. 2. Paroxysmal Atrial Fibrillation: An Ideal Condition to Examine

[figure not shown]
Electrophysiologic Triggers and Diurnal Patterns. PAF is often asymptomatic and occurs early in the continuum of persistent AF development ¹¹. Half of those with PAF have no obvious cause ¹² which may be due to unrecognized triggers such as SDB. The longer PAF persists, the more difficult it is to restore sinus rhythm and prevent recurrence which emphasizes the need to expeditiously identify and address potential contributing factors such as SDB at this stage of disease ¹³. Patients initially presenting with PAF often progress to longer, non-self-terminating bouts ¹³. Importantly, PAF often begins before electrical and extensive structural cardiac remodeling has occurred and provides an ideal substrate for examining acute physiologic triggers such as those that occur in SDB. In individuals with symptomatic PAF, there is a 12:1 ratio of asymptomatic versus symptomatic episodes ¹⁴, therefore continuous ECG monitoring is helpful to provide more detailed, objective data on paroxysms as described in the current proposal. Furthermore, unlike continuous AF, which does not allow reliable detection of autonomic dysregulation via heart rate variability (HRV) indices from ECG data; in PAF, HRV analyses for autonomic function assessment can be derived from the normal sinus rhythm (NSR) period data.

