5. SAMPLE SELECTION

Cases. Patients with PAF who present to Electrophysiology (EP) Clinic at UHCMC and the Cleveland Clinic Foundation (CCF) will be approached for recruitment in the study.

Inclusion Criteria for Cases: 1) *PAF defined by recurrent episodes of AF, which self-terminate within a 7-day period (based upon AHA consensus statement 77)*, 2) Age 18-80 years, 3) Individuals able to participate in ≥ 2 overnight/daytime sleep and physiologic assessments over a 3 month period.

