10. DATA ANALYSIS

EXPOSURES: *Primary:* 1) SDB defined by AHI, i.e. number of apneas + hypopneas/hour of sleep. *Secondary:* 1) Hypoxia: % sleep time with $\text{SaO}_2 < 90\%$, 2) Obstructive Sleep Apnea [obstructive apneas and hypopneas/hour of sleep, obstructive apnea hypopnea index (OAHI)], 3) Central Sleep Apnea [central apneas/hour of sleep, Central Apnea Index (CAI)], 4) Periodic Breathing and 5) EEG arousals [per hour of sleep, Arousal Index (AI)].

OUTCOME: 1) PAF (SA1) and 2) AF burden defined as frequency of AF paroxysms overall and based on self-reported sleep vs. wake (SA2 and 3)

COVARIATES: Age, race, body mass index (BMI, kg/m^2), waist circumference (cm), anti-arrhythmic/beta blocker/calcium channel blocker/ACE inhibitor/angiotensin receptor blocker medications, pacemaker, defibrillator, heart failure (NYHA class), BP, diabetes mellitus, left atrial volume, LVEF, caffeine use, alcohol use and smoking (current versus never smoker or pack years) and activity level. When assessing hypoxia as the relevant exposure, pulmonary disorders will be included as potential confounders.

Table 2. Mediator (SA1) or Outcome (SA3)

Domain	Primary	Secondary	Rationale
Echocardiographic Measures	Left Atrial Volume (ml/m^2)	LA Pressure, LA Systolic Strain, RA area, RA Pressure, LAA Peak Anterograde Flow Velocity (cm/s), Right Atrial Pressure (mmHg), LVEF, LVMI, LVH (concentric LVMI >0.41 , eccentric ≤ 0.41).	Left Atrial Volume predicts risk of AF and PAF ¹⁰³⁻¹⁰⁶ . Secondary measures also associated with AF.
Autonomic Function (Heart Rate Variability)	SDNN (ms) (Time Domain HRV Measure)	Time Domain (r-MSSD (ms), pNN50), Frequency Domain [LF (Hz), HF (Hz), LF/HF], Graphical Parameters (HR patterns, power spectral analysis, Poincaré plots and beat-by-beat HR tachograms) and Novel non-linear measures (e.g. Conditional Entropy ¹⁰⁷).	Reduced SDNN and LF/HF have been identified as AF triggers ⁴⁰ .
Systemic Inflammation	hs-CRP (mg/L)	IL-6 (pg/ml), sIL-6R (ng/mL)	hs-CRP and IL-6 associated with SDB and AF ⁴⁷⁻⁴⁹ . s-IL6R varies with overnight hypoxia ⁴⁶
Oxidative Stress	Endothelin-1 (pg/ml)	Urinary isoprostane 8-epi-prostaglandin F2a (ng/ mmolCr), Oxidized LDL (U/L)	Endothelin-1 implicated in AF ⁵⁷⁻⁵⁹ . Isoprostane ⁶⁰⁻⁶² and oxidized LDL sensitive to SDB ⁷⁶ .

ANALYTIC METHOD BY AIM.

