SA3. For a log-normally distributed outcome, assuming a correlation between pre- and post-PAF burden of 0.8 and a coefficient of variation of 1.5 (based upon prior data ¹¹¹), a sample size of 75 will detect a mean ratio between post and pre PAF burden of 0.83 with 83.1% power based on a paired t-test and a two-sided significance level of 0.05.

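### The aims define PAF burden by frequency and duration, but the analysis carries only a paroxysm count with no rule for continuous AF, so lengthening AF can score as improvement in SA3 and as low burden in SA2

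*Combined protocol and SAP*

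**What the plan says.** The aims, at the end of section 1 (Abstract), give SA2 as: "Examine PAF burden (defined as frequency of paroxysms over a 24 hour period and average duration of paroxysms". Burden there has two components, and SA3 uses the same term.

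The outcome definition, identical in sections 9 and 10, has one component: "AF burden defined as frequency of AF paroxysms overall and based on self-reported sleep vs. wake (SA2 and 3". The SA3 method states "Primary outcome: AF paroxysm frequency from 1-week ECG monitoring". The SA2 model is built on mean paroxysm frequency. In section 8, under continuous ECG monitoring, the technician scores paroxysm frequency and splits it by sleep and wake. Duration appears in none of these places. The SA3 regression that follows the paired test models PAF burden without saying which definition applies.

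Two other statements bear on the point. Section 3.A.2 says "Patients initially presenting with PAF often progress to longer, non-self-terminating bouts". The case definition in section 5 is "PAF defined by recurrent episodes of AF, which self-terminate within a 7-day period", so one qualifying episode can be about as long as a 7-day recording. Neither analysis section says how continuous AF during a recording is counted, or how a participant in that state at 3 months enters SA3.

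**The concern.** A count of paroxysms does not rise steadily with AF severity. It rises as short episodes become more frequent, then falls as episodes lengthen and merge. A recording wholly in AF contains at most one.

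SA3 compares each participant with themselves before and after CPAP, with no untreated group. If sustained AF is more common at follow-up than at baseline and is scored by count, the fall in count goes straight into the apparent CPAP effect. SA3 exists to supply effect sizes and variability for later trials, so the error would be carried into their design.

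SA2 uses baseline recordings only, so progression by month 3 cannot affect it. The related problem there is that participants with few but long episodes sit at the low end of the outcome. That would distort the SDB association if SDB goes with longer episodes, which the documents do not establish either way.

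**Working it through.** **Inputs from the plan (section 10, Power by aim, SA3).** The calculation takes a log-normal outcome, a pre/post correlation of 0.8, a CV of 1.5 and a paired t-test at two-sided 5%. Its result is: "a sample size of 75 will detect a mean ratio between post and pre PAF burden of 0.83 with 83.1% power".

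**Reproducing the plan's figure.** For a log-normal outcome with the correlation read on the raw scale:
- log-scale variance = ln(1 + 1.5²) = 1.179
- log-scale covariance = ln(1 + 0.8 × 1.5²) = 1.030, a log-scale correlation of 1.030/1.179 = 0.874
- SD of the log difference = √[2 × (1.179 − 1.030)] = 0.546
- noncentrality = |ln 0.83| / (0.546/√75) = 2.96
- power, noncentral t with 74 df = 83.1%, as stated.

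Reading 0.8 as the log-scale correlation gives only 64.0%, so the raw-scale reading is used below.

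**Size of the shift.** Assumptions not in the documents: CPAP has no effect; median baseline frequency is b per week; k of 75 participants have sustained AF at follow-up and none at baseline; each of these is scored as 1 per week. The expected apparent ratio is then

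ratio ≈ exp[−(k/75) × ln b].

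Example: b = 10 and k = 6 gives exp(−0.08 × 2.303) = 0.83.

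For the planned analysis I simulated paired log differences and applied Shapiro-Wilk at 0.05 (the plan names no level). The Wilcoxon signed rank test was used on rejection and the paired t-test otherwise. A false decrease is a significant fall when there is no effect; the nominal rate is 2.5%.

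| Median baseline per week | Ratio, k = 4 / 6 / 8 | False decrease, k = 4 / 6 / 8 |
|---|---|---|
| 2 | 0.96 / 0.95 / 0.93 | about 6% / 8% / 10% |
| 5 | 0.92 / 0.88 / 0.84 | about 9% / 14% / 22% |
| 10 | 0.88 / 0.83 / 0.78 | about 10% / 16% / 26–28% |

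The number of one-sided cases needed to produce 0.83 by itself is 75 × |ln 0.83| / ln b: about 20 at 2/week, 9 at 5/week and 6 at 10/week.

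**Sustained AF at both visits.** With 6 such recordings at each visit (different participants), the ratio is 1.00 at every baseline and false decreases do not exceed the nominal 2.5%. With 8 at follow-up and 4 at baseline, false decreases are about 5–6% and the ratio at 5/week is 0.92, the value for a net excess of 4. The bias therefore follows the net excess at follow-up over baseline.

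**The case against.** Several stronger readings are tempting, and the documents do not support them.

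- A reader might infer that duration is absent from the plan altogether. It is in the aims. The documented fault is that the aims and the analysis sections disagree, and duration is lost between them.
- A reader might infer that a participant in sustained AF is scored 0 or 1 and so enters as improved. No such rule exists. The participant could instead be excluded or treated as missing, and a score of 1 is a fall only from a baseline above 1. The alternatives are not safe by default: exclusion removes some of the worst outcomes, and a score of 0 has no logarithm although the power calculation assumes a log-normal outcome.
- A reader might infer that progression within 3 months is expected. Section 3.A.2 gives no time frame or rate. The only time frame for progression to permanent AF is a 21-year cohort cited in section 3.A.3, and section 6 limits approach to patients diagnosed within the last 6 months. Nothing in the documents supports 4 to 8 of 75 as a forecast.
- A reader might quote the paired t-test alone, which gives false decreases of 13% and 43% at 5/week and 19% and 66% at 10/week for k = 4 and 8. Those figures omit the plan's Wilcoxon fallback. At 5/week and above, Shapiro-Wilk rejects in most of these simulated studies, so the lower rates in the table are the relevant ones.

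It is also fair to say that SA3 is declared non-confirmatory, so false-significance rates are secondary. Monitoring elsewhere in the plan runs 7 to 21 days, so a 7-day episode need not fill a recording.

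What stands is the mismatch of definitions, the missing scoring rule, and an endpoint that can fall as AF lengthens.

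**Conclusion.** The point holds as a gap in outcome definition with a conditional bias. The duration component in the aims reaches no outcome definition, named analysis or scoring instruction, and continuous AF has no scoring rule. If the count is applied as written, sustained AF can register as improvement in SA3 for anyone with two or more paroxysms at baseline, and long baseline episodes register as low burden in SA2.

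The size in SA3 depends on the net excess of sustained-AF recordings at follow-up and on baseline frequency, and the documents give neither. Under the one-sided assumption it ranges from minor (at most a 7% apparent reduction at 2/week) to as large as or larger than the planned effect (a 22% reduction with 8 cases at 10/week). It vanishes when the numbers at the two visits are equal. No size can be put on the SA2 distortion. The practical harm is a biased effect size and variance passed to later trials; no confirmatory conclusion is at risk.

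**What to change.** 1. Reconcile the burden definition in the aims with the ECG scoring in section 8, the outcome definitions and SA2/SA3 methods in sections 9 and 10, and the SA3 regression.
2. From the existing continuous recordings, derive percent of analysable recording time in AF, with average episode duration, and name it as an outcome beside frequency in SA2 and SA3. It rises as AF becomes longer or continuous.
3. State how continuous AF is scored, and report the number of participants in AF throughout the recording at each visit. Define this so that a short episode still running when monitoring stops is not caught.
4. Add an SA3 sensitivity analysis giving the worst rank to participants in AF throughout the follow-up recording but not the baseline recording. Keep the paired log-scale estimate for effect size and variance, because a rank analysis yields neither and SA3 is meant to supply both.

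The cost is one derived variable, one extra analysis and SAP wording, with no new data collection. The 83.1% power figure would apply only to the log-frequency t-test.
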